11.4. Skin Care while on Study

Prior to the application of the ATI-502 study medication, the identified AD treatment area should be washed and cleaned using the subject's routine cleansing products. The area should be dried completely prior to the application of the study medication. Subjects must not wash the treatment area, go swimming or perform physical exercise that may cause perfuse sweating for a period of 6 hours after applying the ATI-502 study medication. While on study, subjects should continue to use their routine cleansing and cosmetic products on study.

Subjects may not use a non-therapeutic, bland emollient/moisturizer or sunscreens on the AD target treatment area for the duration of the study. Moisturizers, emollients, and sunscreens may be used on NON-AD target treatment areas. Subjects must take special precautions to try and limit sun exposure to all identified treatment areas by wearing protective clothing and applying sunscreen to NON -AD target treatment areas only.

11.5. Concomitant Medications

Concomitant therapies are any new or existing therapy received from Visit 1 until discharge from the study.

Concomitant therapies include drug (*e.g.*, prescription, over-the-counter [OTC]) and non-drug (*e.g.*, chiropractic, physical therapy, energy-based treatments) therapies. Subjects will refrain from receipt of any therapy in compliance with the inclusion/exclusion criteria. Subjects should refrain from changing the use of any concomitant therapies during the study.

All new or modified concomitant therapies used during the study must be recorded.

Any new or modified concomitant therapy must be considered to determine if it is related to an AE. An AE must be reported unless the therapy is modified for non- medical reasons (*e.g.*, health insurance purposes) or it is for prophylaxis (*e.g.*, vaccinations).

11.6. Prohibited Medications

While subjects are participating in this study they are prohibited from using the following medication/therapies:

- Phototherapy -Subjects must refrain from excessive sunlight (natural or artificial) and must apply sunscreen to all treatment areas if excessive exposure cannot be avoided.
- Systemic immunosuppressant or immunomodulatory therapy (e.g. etanercept, alefacept, infliximab, methotrexate)
- JAK inhibitors (systemic or topical)
- Systemic corticosteroids (intranasal and inhaled corticosteroids are allowed)
- Cytostatic agents
- Crisaborole
- Dupilumab or other monoclonal antibody for the treatment of AD
- Systemic antibiotics
- Topical treatments for atopic dermatitis (corticosteroids, calcineurin inhibitors, topical H1 and H2 antihistamines, topical antimicrobials, and other medicated topical agents)
- Prescription moisturizers
- Topical antibacterial medications or products, including soaps, bleach baths, or topical sodium hypochlorite-based products.
- Vaccine treatments

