⁷ All subjects will be required to have virology testing for HepB (HBsAG), HCV(antibody), and HIV (antibody). If a subject demonstrates to have serological evidence HepB (HBsAG), HCV (antibody) or HIV (antibody), the subject will not be allowed to enroll to the study.

⁸ Canfield staff will review all photographs within 2 days of the photographs being submitted. If a re-take is required, Canfield will notify the site and the re-take photographs will need to be performed within 7 days of the visit. Prior to enrollment to the study, each subject's Visit 1 photos will be reviewed by a panel of board certified dermatologists to ensure that the subject's target areas for treatment meet the study entry criteria. In cases where the photographs do not properly characterize the disease (due to flashback and whitening on the photographs) the subjects will be allowed to enroll to the study based upon the Principal Investigator's clinical assessment of the subject.

⁹ At visit 2, following confirmation that the subject is approved for enrollment to the study, the site will weigh and dispense supplies of ATI-502 study medication and disposable droppers to the subject for at home application of the study medication.

¹⁰ All subjects will have their first application of study medication applied in the clinic during Visit 2. Subjects will continue to apply ATI-502 Topical Solution, 0.46% to all target areas twice a day for 4 weeks (Day 28) unless the subject meets the criteria for treatment interruption. If new areas of AD develop, subjects will be allowed to treat these areas with the ATI-502 study medication.

¹¹ Sites will be required to review with each subject the proper application of the study medication and remind that they must refrain from exercise that may cause excessive sweating, bathing or swimming for a period of 6 hours after the application of study medication. Subjects are also to be reminded that they may not apply moisturizers, emollients, or sunscreen to target AD areas during protocol treatment.

¹² All non-serious AEs will be collected from the time of first study medication application until the final study visit. Serious AEs will be collected from the time of consent through the final study visit.

¹³ A final safety follow up visit will be conducted at week 8 (Visit 6). For those subjects that discontinue the study early, they must return to the clinic 4 weeks following the last study medication application for a final safety visit.

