9. SELECTION AND WITHDRAWAL OF SUBJECTS

9.1. Subject Inclusion Criteria

Subjects must meet the following criteria to be eligible for participation in the study:

1. Able to comprehend and willing to sign an Informed Consent Form (ICF).
2. Male or non-pregnant, non-nursing female subjects ≥ 18 years old at the time of informed consent.
3. Subject must have diagnosis of AD according to the Hanifin and Rajka criteria.
4. Subject must have a diagnosis of moderate (PGA =3) or severe (PGA=4) AD for a period of ≥ 6 months prior to the first dose of study medication (Visit 2).
5. Subject Visit 1 photographs are approved for enrollment by the dermatology review panel.
6. Body surface area involvement must be between 2-20% (excluding scalp, face, palms of hands, soles of feet, groin and genitalia).
7. Subject must have an absolute neutrophil count (ANC) and a platelet count within normal limits
8. Subject must be willing to refrain from washing area of treatment or swimming for 6 hours after each treatment application with ATI-502.
9. Subjects must be willing to refrain from excess of sun exposure.
10. Subject is willing and able to follow all study instructions and be willing to attend all study visits.
11. Subject must refrain from participating in strenuous exercise that would cause profuse sweating for a period of 6 hours after each treatment application with ATI-502.
12. Subject must refrain from using moisturizers, emollients, and sunscreen on target AD treatment area for the duration of protocol therapy.
13. Be in good general health and free of any known disease state or physical condition which, in the investigator's opinion, might impair evaluation of the subject or which might expose the subject to an unacceptable risk by study participation.
14. If a woman of childbearing potential (WOCBP), must have a negative serum pregnancy test at Screening (Visit 1) and a negative urine pregnancy test at Baseline (Visit 2) and agree to: use a highly effective method of birth control for the duration of the study; not be planning a pregnancy during the study duration and use contraception for 30 days after last application of study medication.
15. Sexually active male subjects must agree to use a barrier method of contraception from the first application of study medication to at least 30 days after the last application of study medication.

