19. APPENDICES

APPENDIX 1. SUBJECT INSTRUCTIONS

Preparation and General Instructions:

1. Gather a clean washcloth and towel, the study medication bottle, and disposable dropper.
2. Skin should be clean and dry before applying study medication.
3. Refrain from bathing, swimming and/or participating in strenuous exercise that would cause profuse sweating for 6 hours after application of study medication.
4. Refrain from applying moisturizers, emollients and sunscreen to AD treatment areas for the duration of protocol therapy. Moisturizers, emollients and sunscreens may be applied to non-AD treatment areas.
5. Wash your hands with soap and water before and after using this study medication.
6. Apply a thin layer of study medication to the identified AD target skin area as instructed by the study doctor or the study staff. Keep applying study medication to the area throughout the study, even if the skin begins to clear. If new areas of AD appear, study medication may be applied to these areas.
7. Avoid study medication contact with the eye.
8. You will apply study medication twice-a-day, approximately 12 hours apart.
9. Remember to bring your study medication bottles both used and unused to each study visit.

Study Medication Application:

1. Draw up exactly 1 mL of study medication into the dropper. The medication level should be at the 1mL line.
2. During study medication application, avoid any study medication running into your eyes.
3. Squeeze a few drops of study medication onto the center of the identified target AD area and gently rub the study medication into your skin. Keep applying a few drops and rubbing into your skin until **the entire area** is covered with a thin film of study medication.
4. Draw up additional medication - 1 mL at a time- to cover the entire AD area.
5. Replace the screw top cap and make sure it is closed tightly. Dispose of the used dropper(s).
6. It is important to continue to apply study medication to the target AD areas throughout the study, even if the skin begins to clear.
7. Wash your hands after using this product to prevent any residue being left on your hands.
8. If you missed a dose or doses, tell the study staff at your next visit.

Missed Doses: If you miss a dose of this study medicine, apply it as soon as possible. However, if it is almost time for your next dose, skip the missed dose, and go back to your regular dosing schedule.

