#### **4.1.8 Major Protocol Violations**

Protocol violations will be identified to measure adherence to key aspects the protocol. Prior to analysis, the sponsor will assess the data and identify all protocol violations. Specific data fields that will be examined to identify protocol violations include entrance inclusion/exclusion criteria and prohibited prior and concomitant medications as well as all violations identified by the investigator. All protocol violations will be listed.

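### Protocol Section 11.6 requires sunscreen on all treatment areas when excessive sun is unavoidable, while four other provisions forbid sunscreen on target AD areas without exception

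*Protocol*

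**What the plan says.** The requirement is in Protocol Section 11.6, in the phototherapy item of the list of prohibited treatments. Subjects are to avoid excessive sunlight and "must apply sunscreen to all treatment areas if excessive exposure cannot be avoided". The list opens with "While subjects are participating in this study they are prohibited from using the following medication/therapies", so the instruction runs for as long as the subject is in the study.

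Four other protocol provisions say the opposite for target areas:

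- Section 11.4: "Subjects may not use a non-therapeutic, bland emollient/moisturizer or sunscreens on the AD target treatment area for the duration of the study". The same section deals with sun protection directly. Exposure of the identified treatment areas is to be limited "by wearing protective clothing and applying sunscreen to NON -AD target treatment areas only".
- Inclusion criterion 12, in Section 9.1 and again in the synopsis: "Subject must refrain from using moisturizers, emollients, and sunscreen on target AD treatment area for the duration of protocol therapy".
- Footnote 11 to Table 2, repeated under the schedule in the SAP, has sites remind subjects that "they may not apply moisturizers, emollients, or sunscreen to target AD areas during protocol treatment".
- Appendix 1, general instruction 4, which is addressed to the subject: "Refrain from applying moisturizers, emollients and sunscreen to AD treatment areas for the duration of protocol therapy".

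On protocol violations, SAP Section 4.1.8 states: "Specific data fields that will be examined to identify protocol violations include entrance inclusion/exclusion criteria". It also covers prohibited medications and any violation that the investigator identifies, and everything found is listed.

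**The concern.** One section commands what four others forbid, on the same skin and over the same weeks. A site that reads Section 11.6 and a site that reads Section 11.4 could give opposite advice about treated skin. The product is topical and the primary outcome is safety and tolerability, so what else is put on the treated skin is more than an editorial matter.

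There is also a compliance side. A subject who does what Section 11.6 demands on a target area departs from inclusion criterion 12. A subject who keeps to Appendix 1 fails a mandatory instruction in Section 11.6. Protocol Section 15.3 keeps eligibility matters out of the milder deviation category, so the first of these, if recorded, would probably be treated as a violation.

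**Working it through.** No arithmetic applies, and the plan gives no figure to reproduce. The check is to set the provisions side by side by area, period and exception.

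| Provision | Instruction on sunscreen | Area | Period | Exception for unavoidable sun |
|---|---|---|---|---|
| Section 11.6 | required if excessive sun is unavoidable | all treatment areas | participation in the study | not applicable |
| Section 11.4 | forbidden | target AD area | whole study | none |
| Inclusion 12 | forbidden | target AD area | protocol therapy | none |
| Table 2, footnote 11 | forbidden | target AD areas | protocol treatment | none |
| Appendix 1, item 4 | forbidden | AD treatment areas | protocol therapy | none |

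**Area.** Target areas are treatment areas, so they fall within the word *all* in Section 11.6. The bans are not identical in reach. Sections 11.1 and 11.2 allow newly appearing AD to be treated, and Sections 12.2 and 12.4 keep such areas apart from the baseline target areas. Three of the four bans name target areas only. Appendix 1 alone is wide enough to take in newly treated areas. What all four share is the target areas, and there each contradicts Section 11.6.

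**Period.** The stated durations differ, but all five provisions apply during the four weeks of treatment (Section 7.4). The wording of Section 11.4 extends beyond treatment, so it also overlaps Section 11.6 outside those weeks. The point does not depend on that.

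**Can the texts be reconciled?** Two readings were tried.

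1. *Section 11.6 is a narrow exception for unavoidable exposure.* None of the bans states an exception or refers to Section 11.6. Section 11.4 takes up the same subject, sun on the treatment areas, and its answer is clothing plus sunscreen on non-target skin only. The word *only* leaves no room for the exception.
2. *Section 11.6 means newly treated, non-target areas.* It says all areas, not new ones. Even for new areas, it would still clash with Appendix 1.

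Neither reading works. For a target area during treatment, a subject with unavoidable excessive exposure must break one rule or the other.

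**Could obeying Section 11.6 surface as a violation?** Table 2 schedules the check of inclusion and exclusion criteria at Visits 1 and 2 only. Sunscreen is not itself an entry in the prohibited list of Section 11.6, and neither document describes a data field for sunscreen use. An investigator could still report such use, and Section 9.3 contemplates a later loss of compliance with an entry criterion. A listing is therefore possible but not assured.

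**Would a listing change an analysis?** Under SAP Section 4.1.1, the Safety and Efficacy Populations need one application of study medication and the Per-Protocol Population needs completion of Visit 6. None of the three is defined by protocol violations.

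**The case against.** The strongest reply is that the conflict hardly ever comes into play. Inclusion criterion 9 requires willingness to avoid excess sun. Section 11.4 already asks for protective clothing. Section 11.1 keeps the face, scalp, palms, soles and groin region out of the target areas, so most target skin can be covered. Subjects receive Appendix 1 and sites give the footnote 11 reminder, and both carry only the ban. This stands, and it is why the point is minor. It does not make the two instructions compatible.

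A second reply is that the documents do not say which rule the sponsor intended, so removing the sunscreen duty is a choice. That is fair. The choice recommended here follows the section written specifically on skin care, and it agrees with the other three bans on target areas.

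Three stronger readings are tempting and are not supported:

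- A reader might infer that a subject who follows Section 11.6 is bound to appear in the violation listing. With no sunscreen field described and eligibility checked only at Visits 1 and 2, *could* is the most that can be said.
- A reader might count the days on which the provisions overlap and treat the total as the size of the problem. Such a count measures calendar time, not exposed subjects or harm.
- A reader might infer bias in the efficacy or safety summaries. Nothing in either document shows an effect on populations, responder rates or conclusions.

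**Conclusion.** The protocol is wrong as written on this point. Section 11.6 and the four bans cannot all be followed for target AD areas during the four-week treatment period when excessive sun cannot be avoided. The importance is low: a correction worth making, not one on which the trial's findings depend.

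The number of subjects who would meet the condition is not given and none is claimed. That it is uncommon is an inference from the sun-avoidance and clothing requirements and from the sites excluded as target areas, not a figure in the documents. The conclusion also rests on the ordinary reading that target areas are among all treatment areas.

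**What to change.** In Protocol Section 11.6, replace the phrase "must apply sunscreen to all treatment areas if excessive exposure cannot be avoided" with wording to this effect: *must protect all treatment areas with protective clothing when excessive sun is unavoidable; sunscreen must not be applied to target AD treatment areas (see Section 11.4)*. This keeps the sun-protection purpose, uses the measure that Section 11.4 already prescribes, and leaves the ban on target areas as the single rule.

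The replacement deliberately stops at target areas. If the sponsor also wants to bar sunscreen from newly treated non-target areas, as Appendix 1 implies, then Section 11.4, inclusion criterion 12 (both places) and footnote 11 must be widened to say so, along with the copy of footnote 11 in the SAP. If the sponsor instead wants sunscreen on target skin in unavoidable sun, all four bans need an explicit exception.

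The recommended change costs one phrase in a protocol amendment, with the ethics approval that Sections 17.1 and 17.4 require before use. It needs no SAP change and no new case report form item, visit or subject.

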11.7. Treatment Compliance

The investigator or designee will be responsible for monitoring subject compliance through questioning the subject, documenting missed doses, if any, weighing the bottle before dispensing and after return and visual inspection of the quantity in the study medication bottles (used and unused). Study staff will counsel the subjects, as required to make sure subjects are compliant with study medication applications.

12. STUDY ASSESSMENTS

12.1. Physician's Global Assessment (PGA)

The PGA is the investigator's assessment of the average overall severity of subject's AD at a particular point in time. At every study visit, the investigator will assess the PGA using the scale below and report the one integer that best describes the average overall severity of each target evaluation area of AD per subject. One assessment will be conducted for each target treatment area.

Table 5: Physician's Global Assessment

PHYSICIAN'S GLOBAL ASSESSMENT	
Grade	Descriptor
0	Clear: No erythema or induration; no oozing/crusting; barely perceptible residual post-inflammatory hypo- or hyperpigmentation may be present
1	Almost Clear: Minimal light red erythema and/or induration; no oozing/crusting
2	Mild: Light red erythema with mild induration; no oozing/crusting
3	Moderate: Red erythema with moderate induration; oozing/crusting may be present
4	Severe: Bright or deep red erythema with severe induration; oozing/crusting present

12.2. Body Surface Area (BSA)

For this study, 1% Body Surface Area (BSA) is defined as the area of the subject's hand with the fingers and thumb together. The subjects are required to have 2-20% total BSA of active AD to be enrolled in the study. Body surface area of each target treatment area will be assessed at each treatment visit. If new areas of AD develop while the subject is on study, these new areas will not be assessed.

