6.2. Secondary Outcome Measures

The secondary outcome measures for this study are to assess the following:

- Change from baseline in Physician Global Assessment (PGA) score following 4 weeks of treatment with ATI-502 Topical Solution, 0.46%
- Change from baseline in body surface area affected by atopic dermatitis following 4 weeks of treatment with ATI-502 Topical Solution, 0.46%.
- Change from baseline in Eczema Area and Severity Index (EASI) score following 4 weeks of treatment with ATI-502 Topical Solution, 0.46%.
- Change from baseline in the subjects Signs of Atopic Dermatitis (SAD) assessment following 4 weeks of treatment with ATI-502 Topical Solution, 0.46%.
- Change from baseline in Subjects Pruritis Assessment (SPA) score following 4 weeks of treatment with ATI-502 Topical Solution, 0.46%.

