7. INVESTIGATIONAL PLAN

7.1. Overall Study Design

This is an open label, multicenter, phase 2a study designed to evaluate the safety and tolerability of ATI-502 Topical Solution, 0.46% in male and female subjects with a diagnosis of AD as defined by the Hanifin and Rajka criteria. Based on the 5-point Physician's Global Assessment (PGA) scale, subjects must have a score of 3 (moderate) or 4 (severe). Subjects will be required to apply ATI-502 study medication to their identified AD treatment areas twice a day (BID) for a total of 4 weeks. Subjects will be allowed to treat new disease areas with ATI-502 Topical Solution, 0.46% if they appear after Visit 2. All subjects will be required to complete a safety follow up visit 4 weeks post last study medication application.

A total of 30 evaluable subjects who are \geq 18 years of age with a clinical diagnosis of moderate or severe AD will be enrolled to the study.

Subjects will be required to complete the following treatment visits:

- Visit 1: Screening and Photographs for Study Entry Approval
- Visit 2: Study Enrollment and First Treatment with Study Medication
- Visit 3: Follow up Visit
- Visit 4: Follow up Visit
- Visit 5: Follow up Visit
- Visit 6: End of Study Visit

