11. TREATMENT OF SUBJECTS

11.1. Identification of Target Treatment Area

At Visit 1 and Visit 2, the investigator will identify a target treatment area(s) that meets all inclusion criteria (e.g. a diagnosis of AD based on the criteria of Hanifin and Rajka, BSA between 2-20%, and a PGA score of 3 or 4). The target treatment area can not include the scalp, face, palms of hands, soles of feet, groin or genitalia. The investigator will record the identified target treatment area on the body map in the subject's source documents and eCRF. These target treatment areas will be photographed at each specified protocol time point (Refer to [Table 2](#)). Sites will use colored stickers to mark the treatment areas prior to the photographs being taken. (Refer to Section [12.6](#) for photography instructions)

If new areas of atopic dermatitis develop while the subject is on study, these areas may be treated with the ATI-502 study medication (excluding the face, scalp, soles of feet and palms of hands). The treating investigator must identify these new treatment areas at a treatment visit (Visit 2, 3 or 4) to ensure that the area meets the protocol defined treatment criteria. These new treatment areas will be documented in the subject's source documents and in the eCRF.

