12.3. Eczema Area and Severity Index (EASI)

Investigators will use the EASI to assess each subject's extent and severity of atopic dermatitis at Visit 1 and then at every protocol defined treatment visit.

The EASI divides the subject's body down into four body regions:

- Head and Neck
 - Face occupies 33% (17% each side), neck 33% (17% front and back) and scalp 33% of the head and neck region
- Trunk (including genital areas)
 - Front occupies 55% and back 45% of the trunk
- Upper limbs

- Each arm occupies 50% of the upper limbs region (front or back of one arm is 25%)
- Lower limbs (including buttocks)
 - Each leg occupies 45% (front or back of one leg is 22.5%) and buttocks 10% of the lower limbs region

An area score is recorded for each of the four regions of the body. The area score is the percentage of skin affected by AD for each body region.

Table 6: Area Score

Area Score	Percentage of skin affected by AD in each region
0	No active AD in this region
1	1-9%
2	10-29%
3	30-49%
4	50-69%
5	70-89%
6	90-100%; the entire region is affected by AD

The severity score is recorded for each of the four regions of the body. The severity score is the sum of the intensity scores for four signs. The four signs are:

- Redness (erythema, inflammation)
- Thickness (induration, papulation, swelling-acute AD)
- Scratching (excoriation)
- Lichenification (lined skin, furrowing, prurigo nodules-chronic AD)

The *AVERAGE* intensity of each sign in each body area is assessed according to the following table:

Table 7: Severity Score

Score	Intensity of redness, thickness/swelling, scratching, lichenification
0	None, absent
1	Mild (just perceptible)
2	Moderate (obvious)
3	Severe

Half scores are allowed. In darker skin type subject's, it may be difficult to assess redness and in this case increase the average redness score by 1 level.

Table 8: Four signs of AD used to calculate EASI severity score

Intensity	None	Mild	Moderate	Severe
Redness				
	Score 0	Score 1	Score 2	Score 3
Thickness/induration papulation/oedema				
	Score 0	Score 1	Score 2	Score 3
Scratching				
	Score 0	Score 1	Score 2	Score 3
Lichenification/prurigo				
	Score 0	Score 1	Score 2	Score 3

(Hanifin, 2001)

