#### **4.2.4 Body Surface Area of AD**

The body surface area of AD will be summarized descriptively (N, mean, SD, median, minimum and maximum) for the absolute BSA, change, and percent change from baseline by visit. Change will be computed as the timepoint score – baseline score. Percent change as  $100 * \text{change} \div \text{baseline}$ .

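### BSA is named as the area affected by AD but measured only on baseline target areas; leaving out new areas shifts the reported change by zero or towards improvement

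*Protocol*

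**What the plan says.** Protocol 6.2 lists as a secondary outcome "Change from baseline in body surface area affected by atopic dermatitis following 4 weeks of treatment". The synopsis and SAP 1.2 do the same. SAP 4.2.4 keeps the unrestricted label, "The body surface area of AD will be summarized descriptively", and tabulates absolute value, change and percent change by visit.

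Protocol 12.2 is narrower. BSA is taken for each target treatment area, and "If new areas of AD develop while the subject is on study, these new areas will not be assessed".

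New disease is expected. Protocol 7.1 states: "Subjects will be allowed to treat new disease areas with ATI-502 Topical Solution, 0.46% if they appear after Visit 2". Protocol 11.1 has new treatment areas documented in the source and eCRF, but does not ask for their size, and it limits when they are identified: "The treating investigator must identify these new treatment areas at a treatment visit (Visit 2, 3 or 4".

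The anatomical limits also differ. For baseline, protocol 9.1 says "Body surface area involvement must be between 2-20% (excluding scalp, face, palms of hands, soles of feet, groin and genitalia". For new areas, protocol 11.1 says "these areas may be treated with the ATI-502 study medication (excluding the face, scalp, soles of feet and palms of hands", which does not mention groin or genitalia.

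**The concern.** BSA is a measure of extent, and new lesions are part of extent. A reader of the results table will take the BSA row as change in how much skin has AD. Under protocol 12.2, a subject whose target areas shrink while new areas appear elsewhere is reported as improved by the full target-area reduction. The study is single-arm and open-label, so no control group carries the same omission and offsets it.

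The omission cannot reliably be repaired afterwards. The size of new areas is not requested. The visits listed for identifying them stop at Visit 4, and so leave out Visit 5, the Week 4 visit at which this outcome is read, and Visit 6.

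**Working it through.** The plan gives no figure to reproduce: N = 30 has no formal basis (SAP 4.4) and no inference is planned (protocol 14.1). The check is therefore on direction and leverage.

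**Inputs**
- T0, baseline target-area BSA: 2% to 20% at entry (protocol 9.1 and 12.2).
- T1, target-area BSA at the visit.
- W ≥ 0, BSA of areas that arose after baseline and are present at the visit, at sites eligible for baseline BSA. The documents give no rate or size, so W is assumed below.
- Visit days 15 and 29, each ± 3 days (protocol Table 2).
- The target areas are taken to be all the eligible AD present at baseline.

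**Direction**
- Measured change = T1 − T0.
- Named change = (T1 + W) − T0.
- Measured minus named = −W BSA points, or −100 × W / T0 percentage points.

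Each subject's value moves towards improvement or not at all, so the group mean and median do too.

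**Leverage of one BSA point (W = 1), with target areas assumed to halve**

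| T0 | 100 × W / T0 | Reported change | With new area counted |
|---|---|---|---|
| 2% | 100 × 1 / 2 = 50 | −50% | 0% |
| 10% | 100 × 1 / 10 = 10 | −50% | −40% |
| 20% | 100 × 1 / 20 = 5 | −50% | −45% |

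**Group mean, 30 subjects (assumed: 3 to 15 subjects with new areas of 1 to 2 points each)**
- Low end: 3 × 1 / 30 = 0.1 BSA points.
- High end: 15 × 2 / 30 = 1.0 BSA points.

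Shift in mean percent change, with W = 1 and the same T0 for all subjects:

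| T0 | 3 of 30 affected | 15 of 30 affected |
|---|---|---|
| 2% | 3 × 50 / 30 = 5 | 15 × 50 / 30 = 25 |
| 10% | 3 × 10 / 30 = 1 | 15 × 10 / 30 = 5 |
| 20% | 3 × 5 / 30 = 0.5 | 15 × 5 / 30 = 2.5 |

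**Gap in identifying new areas**
- Nominal, Visit 4 to Visit 5: 29 − 15 = 14 days, half of the 28 treatment days.
- Shortest with windows: (29 − 3) − (15 + 3) = 8 days.
- Longest with windows: (29 + 3) − (15 − 3) = 20 days.

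Protocol 11.1 does not require a new area that first appears in this interval to be recorded.

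**The case against.** **The limit is stated openly and fits the design.** Protocol 12.2 is explicit, and SAD, SPA and PGA are also scored by target area. Following the same lesions is a defensible choice. That stands as a defence of the measurement but not of the label. SAD, SPA and PGA rate severity within an area, whereas BSA is an extent measure. Neither the outcome name nor the SAP carries the restriction.

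**EASI already covers the whole body.** This stands in part. In EASI, "The area score is the percentage of skin affected by AD for each body region", it is scored at every visit, and new AD of at least 1% in a previously clear region must raise that region's area score from 0. But the bands are wide: a region going from 10% to 29% affected keeps area score 2. EASI is also a composite and does not correct the BSA table. Outward spread of a target area does count in target BSA, so only separate new areas are lost.

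**The direction is conditional.** Protocol 11.1 does not say that every eligible lesion must be a target area. If non-target AD exists at baseline, the percentage denominator changes, and change in that disease is a second omission that could go either way. The part due to new areas keeps its sign.

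Protocol 11.1 also lists Visit 2 among the visits for identifying new areas. A lesion of 2 points left out of a 10-point baseline that then cleared, while the target areas halved, would give −5/10 = −50% reported against −7/12 = −58%. That reading is weak: protocol 11.1 and Table 2 set target areas at Visit 2, and protocol 7.1 places new areas after it.

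**The size is assumed.** True. The 25-point figure needs half the subjects to develop new disease and all 30 to sit at the 2% floor. At 10% to 20% baseline BSA, the same assumptions give 0.5 to 5 points.

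**Conclusion.** The concern holds. A plan followed to the letter reports a change that differs from the named outcome by −W BSA points. This is zero for subjects with no new area and favourable for the rest. The sign follows from the definitions. The size cannot be derived from the documents: 0.1 to 1.0 BSA points in the group mean is an illustration under the stated assumptions. The effect on percent change is largest in subjects who enter near 2%.

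This should be corrected, but it is not critical. BSA is a descriptive secondary outcome, no test or sample size depends on it, and the primary outcome is safety. Correcting it would not remove regression to the mean from selecting subjects on severity at entry, which is a separate limit of the design.

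**What to change.** **Preferred.**
- In protocol 12.2, record the % BSA of new AD areas, by the same handprint method, at Visits 3 to 6, including Week 4, whether or not the area is treated.
- Restrict this to the body sites that count towards baseline BSA under inclusion criterion 6, and state the restriction, because the site list for new areas in 11.1 does not match it. This concerns measurement only, not where to treat.
- In SAP 4.2.4, report change in BSA over eligible sites (target plus new) beside target-area BSA, with the number and percentage of subjects with any new area.

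**Fallback**, if new-area size cannot be collected or was not collected for subjects already treated. Rename the outcome as BSA of baseline target areas in protocol 6.2 and SAP 1.2 and 4.2.4. Report beside it the number of subjects with documented new areas, noting that areas first appearing after Visit 4 may be missed.

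**Cost.** The preferred option adds one small data field at four visits where whole-body EASI is already scored, and short wording changes. At Visits 5 and 6 the check for new areas is an added task, because 11.1 does not list those visits. The BSA result may become less favourable, by the mean of W. The fallback costs wording and a count.
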